6.2.1.1. Mean Daily OCS Dose

The change in the mean daily OCS dose from Weeks 0-4 to Weeks 48-52 will be calculated as follows:

The mean daily OCS dose for weeks 0-4 will be calculated as:

$$\frac{\text{Sum of daily OCS dose for weeks 0 – 4}}{28}$$

The mean daily OCS dose for weeks 48-52 will be calculated as:

$$\frac{\text{Sum of daily OCS dose for weeks 48 – 52}}{28}$$

The change in the mean daily OCS dose from Weeks 0-4 to Weeks 48-52 will be the difference of mean daily OCS dose for weeks 48-52 minus mean daily OCS dose for Weeks 0-4.

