4.3. Secondary Efficacy Endpoint Analyses

All secondary endpoints will be summarised descriptively. Each four-week period from Weeks 0-4 through to Weeks 48-52 is shown in Section 6.2.4.2.

4.3.1. Change in the mean daily OCS dose (prednisone/prednisolone or equivalent) from Weeks 0 to 4 to Weeks 48 to 52

Derivation of Endpoint

For each participant, the OCS dose on each day of the study will be identified from the concomitant medications data (see Section 6.2.1). The mean daily OCS (prednisone or equivalent) dose for each 4-week period (Weeks 0-4 through to Weeks 48-52) for each participant will be calculated as the sum of the daily doses of OCS during each period divided by the total number of days (see Section 6.2.1.1).

Participants withdrawing from the study prematurely will have mean daily OCS (prednisone or equivalent) dose calculated using available data up to study withdrawal date only (divided by the number of days for which there is available data).

The change in the mean daily OCS dose from Week 0 to 4 to Week 48 to 52 will be calculated for each participant as the mean daily OCS dose for Week 48 to 52 minus the mean daily OCS dose for Week 0 to 4. The change in the mean daily OCS dose from Week 0 to 4 to each 4-week period from Weeks 4-8 through to Weeks 48-52 will be calculated using the same formula.

The estimand for this endpoint is described in Section 1.1 and summarised below.

Target Participant Population	Participants with HES aged 6 to 17 years that are taking OCS at baseline, i.e. mean Week 0 to 4 OCS dose >0 mg/day.
Endpoint	Change in the mean daily OCS dose (prednisone/prednisolone or equivalent) from Weeks 0 to 4 to Weeks 48 to 52.
Intercurrent events	The anticipated intercurrent events and corresponding strategies are:- 
 • Study treatment discontinuation: treatment policy strategy. • Changes to OCS therapy: composite strategy (part of endpoint). • Other changes to background HES medication which might modulate the disease course of HES, determined either by published data or by proposed or known mechanism of action: treatment policy strategy.
Summary measure	Mean change from Weeks 0 to 4 to Weeks 48 to 52 across participants.

Main analytical approach

Summary statistics for mean daily OCS (prednisone or equivalent) dose for each 4-week period from Weeks 0-4 through to Weeks 48-52 will be presented by treatment group, including change in the mean daily OCS dose.

Additional Estimands

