6.2. Appendix 2: Data Derivations Rule

6.2.1. Oral Prednisone/Prednisolone or Equivalent Daily Dose

For each subject, oral prednisone equivalent daily dose (mg) on each day of the study will be identified from the concomitant medications form. Corticosteroids will be identified from the list of coded concomitant medications for the study, by merging with the GSK respiratory medication class (RMC) reference data set by component code. This reference data is created by dictionary specialists who identify a list of component terms for corticosteroids, which then undergo clinical review to ensure the correct classification is assigned.

Only corticosteroids recorded with route = “Oral” will be considered as oral corticosteroids. Subjects not receiving OCS therapy on any day of the study will be assigned a prednisone equivalent daily dose of 0 mg for that day. The corticosteroid conversion factors in the table below will be used to scale each corticosteroid dose to a prednisone equivalent dose.

Medication Name	Scaling Factor
Betamethasone	8.33
Budesonide ¹	0
Cortisone	0.2
Dexamethasone	6.67
Deflazacort	0.83
Hydrocortisone	0.25
Methylprednisone	1.25
Meprednisone	1.25
Prednisone	1
Prednisolone	1
Prednisone acetate	1
Triamcinolone	1.25

¹Budesonide has negligible systemic exposure and will be classed as “Other HES therapy” rather than oral corticosteroid therapy.

Where the frequency of the recorded corticosteroid dose is not once daily, the following calculations will be used to determine the daily dose.

Medication Frequency	Daily Dose Equivalent
BID	2 x dose
TID	3 x dose
QID	4 x dose
QOD	dose / 2
2XWK	(2 x dose) / 7
3XWK	(3 x dose) / 7
4XWK	(4 x dose) / 7
5XWK	(5 x dose) / 7

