6.2.4.2. Medication Assessment Windows

For the reporting of medication use and changes in medication use (e.g. change in OCS dose and change in immunosuppressive and/or cytotoxic HES therapy) will be assigned to a 4-weekly analysis time point according to the table below.

Table 4 Medication Assessment Windows

Reporting Period	First Day Included	Last Day Included
Pre-treatment	Medication is taken on the date of first dose of IP (Day 1)	
Weeks 0-4 (Baseline)	Day after day of first dose	28 days after day of first dose
Weeks 4-8	29 days after day of first dose	56 days after day of first dose
Weeks 8-12	57 days after day of first dose	84 days after day of first dose
Weeks 12-16	85 days after day of first dose	112 days after day of first dose
Weeks 16-20	113 days after day of first dose	140 days after day of first dose
Weeks 20-24	141 days after day of first dose	168 days after day of first dose
Weeks 24-28	169 days after day of first dose	196 days after day of first dose
Weeks 28-32	197 days after day of first dose	224 days after day of first dose
Weeks 32-36	225 days after day of first dose	252 days after day of first dose
Weeks 36-40	253 days after day of first dose	280 days after day of first dose
Weeks 40-44	281 days after day of first dose	308 days after day of first dose

Reporting Period	First Day Included	Last Day Included
Weeks 44-48	309 days after day of first dose	336 days after day of first dose
Weeks 48-52	337 days after day of first dose	364 days after day of first dose

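### SAP 6.2.1.1 divides the mean daily OCS dose by a fixed 28 days, against the days-with-data rule for premature withdrawals in SAP 4.3.1; read literally, it can turn a constant dose into a response

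*SAP*

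**What the plan says.** SAP 6.2.1.1 gives two formulas, both with a fixed divisor: "Sum of daily OCS dose for weeks 0 – 4}}{28" for the first window and "Sum of daily OCS dose for weeks 48 – 52}}{28" for the last. It mentions no incomplete window and gives no formula for the windows in between.

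SAP 4.3.1 defines the mean for every 4-week period as the sum of daily doses "divided by the total number of days (see Section 6.2.1.1", so it names 6.2.1.1 as the calculation. Its next paragraph says that for premature withdrawals the mean is calculated "using available data up to study withdrawal date only (divided by the number of days for which there is available data".

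Both responder endpoints (SAP 4.3.2, reduction of at least 50%; SAP 4.3.3, mean of 7.5 mg/day or less) take their mean from 4.3.1. A withdrawn participant is counted as a failure only if there are no data at all in the window. A partly observed window yields a calculated mean.

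Under SAP 6.2.1, a participant not receiving OCS on a study day "will be assigned a prednisone equivalent daily dose of 0 mg for that day". The SAP text available for review does not say how an OCS record still ongoing at last contact, or a day after last contact, is to be treated.

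**The concern.** The appendix formula and the endpoint section give different numbers for the same participant. Days that were never observed add nothing to the sum but stay in a divisor of 28, so the mean falls. A lower mean is the favourable direction for all three OCS measures: change in dose, reduction of at least 50%, and 7.5 mg/day or less. The rule that counts withdrawals as failures does not catch this, because it needs an empty window. With about 15 participants, one misclassified child visibly moves a reported proportion.

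The withdrawal rule in 4.3.1 also does not extend to completers. The last medication window is fixed in days from first dose, whereas the Week 52 visit may fall up to 7 days early (Protocol 1.3, Table 1). A participant whose first expanded-access dose comes before the follow-up visit does not need that visit (Protocol 6.6), so the last days of the window can lie after the final study contact.

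**Working it through.** **Reproducing the plan's figure.** In SAP Table 4 (6.2.4.2) the last window runs from "337 days after day of first dose" to "364 days after day of first dose": 364 - 337 + 1 = 28 days. The Weeks 0-4 window runs from 1 to 28 days after first dose, also 28 days. The divisor is right for a complete window; the question is only what happens when the window is incomplete.

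**Formulas.** Take a constant dose D mg/day, a complete Weeks 0-4 window (mean D), and k observed days in Weeks 48-52.

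- Fixed divisor (6.2.1.1): mean = D x k/28; change = (k/28 - 1) x 100%.
- Days with data (4.3.1): mean = D x k/k = D; change = 0% for every k.

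**Thresholds under the fixed divisor.**

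- Reduction of at least 50%: k/28 <= 0.5, so k <= 14, meaning that data end by day 350 after first dose (337 + 13).
- Mean of 7.5 mg/day or less: D x k/28 <= 7.5, so D <= 210/k. The result is false when D is above 7.5.

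| Observed days k | Apparent change, constant dose | Largest constant dose scored as 7.5 mg or less | Apparent mean at 10 mg/day |
|---|---|---|---|
| 28 | 0% | 7.50 | 10.00 |
| 24 | -14.3% | 8.75 | 8.57 |
| 21 | -25.0% | 10.00 | 7.50 |
| 20 | -28.6% | 10.50 | 7.14 |
| 14 | -50.0% | 15.00 | 5.00 |
| 10 | -64.3% | 21.00 | 3.57 |
| 7 | -75.0% | 30.00 | 2.50 |

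**Withdrawal example.** At a constant 10 mg/day with 14 observed days, 10 x 14/28 = 5.0 mg/day. The participant meets both responder criteria and contributes a change of -5 mg/day, although the dose never changed. Under 4.3.1 the mean is 10 mg/day, the change is zero and neither criterion is met.

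**Early-visit completer.** A Week 52 visit 7 days early falls at 364 - 7 = 357 days after first dose. This leaves 357 - 337 + 1 = 21 observed days counting the visit day, or 20 without it. If OCS records stop at that visit, a constant 10 mg/day gives 10 x 21/28 = 7.5 mg/day and is scored as a success. If an ongoing record is carried to day 364, the mean is 10 mg/day and there is no bias. In neither case can the visit window produce a 50% reduction at constant dose, since 21 (or 20) is above 14.

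**Weight of one participant.** 1/15 = 6.7 percentage points. The size of the OCS-at-baseline subset is not stated; assuming 5 to 10 participants, one is 20 to 10 points (12.5 points at 8).

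**The case against.** **Section 4.3.1 is the more specific rule.** It deals expressly with premature withdrawals, and both responder endpoints refer to it. An analyst who treats it as overriding the appendix misclassifies no withdrawal. This largely stands: the withdrawal error arises only if 6.2.1.1 is programmed as written. But 4.3.1 itself sends the reader to 6.2.1.1, and nothing states precedence.

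**OCS dose does not come from a diary that stops at the visit.** It is derived from concomitant-medication records with start and end dates (Protocol 6.8; SAP 6.2.1). A drug without an end date still counts as concomitant (SAP 6.2.2.4), and the 0 mg rule is worded for participants not receiving OCS, not for days without a record. Completers outside expanded access have a follow-up visit at which OCS use is recorded. This stands too, and it makes the completer problem conditional and narrow. It does not remove it, because the date rules in SAP 6.2.6 cover partial dates, not ongoing records.

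**Part of SAP 4.1.2 is redacted.** The version history says that handling of medication data within windows was clarified, so relevant text may be hidden. The conflict between the two visible sections does not depend on it.

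**A stronger reading is tempting.** A reader might infer that the plan will routinely score participants on steady doses as responders, or that an early Week 52 visit puts all three OCS endpoints at risk. The documents support neither. The withdrawal effect needs a literal reading of the appendix, and the visit window alone cannot reach the 50% criterion. The divisor of 28 is not an arithmetic error for a complete window.

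**Conclusion.** SAP 6.2.1.1 is wrong as written for incomplete windows and contradicts SAP 4.3.1. The direct conflict concerns participants who withdraw within a 4-week window, and for the endpoints themselves within Weeks 48-52. Programmed literally, the error always lowers the mean: at constant dose it gives a false 50% reduction at 14 or fewer observed days, and a false result of 7.5 mg or less for constant doses above 7.5 and up to 210/k mg/day.

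The second part is weaker. It affects only expanded-access entrants with an early Week 52 visit, and only if their ongoing OCS records are not carried to day 364.

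These endpoints are secondary, descriptive and untested, and the primary flare rate is unaffected. The number of participants involved is probably small: Protocol 9.4.1 expects little missing data, although it says so for the primary endpoint. The documents give no expected count. The point merits correction before database lock because the error runs towards success and each participant carries much weight.

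**What to change.** In SAP 6.2.1.1:

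1. Replace 28 with the number of days from the start of the window to the earlier of the window end and the participant's last day of concomitant-medication recording. This equals 28 when the window is complete. Apply it to every 4-week window and all participants, completers included.
2. State that days after that date are left out of both numerator and denominator and are not set to 0 mg.
3. State that an OCS record ongoing at last contact counts as taken through that date.

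Align the divisor wording in SAP 4.3.1 so that both sections give one rule. The cost is a few sentences in the SAP and a programming check. No data collection changes, and results for complete windows stay the same.

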6.2.2. Study Period

Assessments and events will be classified according to the time of occurrence relative to the study treatment period.

6.2.2.1. Treatment Phases for HES Flare

Study Phase	Definition
Pre-Treatment	Flare onset date < Date of first dose of study treatment
On-Treatment	Date of first dose of study treatment ≤ Flare onset date ≤ Date of last dose of study treatment + 28 days
Off-Treatment	Date of last dose of study treatment + 28 days < Flare onset date ≤ Date of Week 52 visit /Study withdrawal date
Post-Treatment	Flare onset date > Date of Week 52 visit

6.2.2.2. Treatment Phases for other Efficacy Assessments

Study Phase	Definition
Pre-Treatment	Assessment date ≤ Date of first dose of study treatment
On-Treatment	Date of first dose of study treatment < Assessment date ≤ Date of last dose of study treatment + 28 days
Off-Treatment	Date of last dose of study treatment + 28 days < Assessment date ≤ Date of Week 52 visit /Study withdrawal date
Post-Treatment	Assessment date > Date of Week 52 visit

6.2.2.3. Treatment Phases for Adverse Events

Study Phase	Definition
Pre-Treatment	AE onset date/time < Date/time of first dose of study treatment
On-Treatment	Date/time of first dose of study treatment ≤ AE onset date/time ≤ Date of last dose of study treatment + 28 days
Post-Treatment	AE onset date > Date of last dose of study treatment + 28 days

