The secondary estimand for fatigue severity will use the subpopulation of participants with HES aged 12 to 17 years. Treatment condition will be the same as for the primary estimand. A treatment policy strategy will be used for the intercurrent events of study treatment discontinuation and changes to background HES therapy. The endpoint will be the change from baseline in weekly average score of the BFI item 3 (worst level of fatigue during past 24 hours) for Week 52 and the summary measure will be the mean value.

Overall Design:

This is a 52-week, open-label, single arm, multicentre study of SC mepolizumab in children and adolescent participants with HES receiving SoC therapy.

Brief Summary:

The purpose of this study is to investigate the efficacy and safety of SC mepolizumab in paediatric participants aged 6 to 17 years with HES.

Approximately 15 participants who are on a stable dose of HES therapy for at least 4 weeks prior to Visit 2 will be enrolled. All eligible participants will receive mepolizumab, with the first dose administered at Visit 2, and subsequent doses administered every 4 weeks over a treatment period of 52 weeks (with a last dose at 48 weeks).

Concomitant SoC therapy may be adjusted as needed from 4 weeks after the first dose of mepolizumab. All participants will be managed during the study according to routine medical care.

All participants will attend a study-site visit at Screening (Visit 1), Baseline (Visit 2), Week 4 (Visit 3), Week 8 (Visit 4), Week 24 (Visit 8), and the Week 52 exit visit (Visit 15). The other study visits may be performed remotely where applicable country and local regulations allow. Home healthcare services may also be utilised to support these activities where local regulations and infrastructure allow. The final visit of the treatment period will be at Week 52. There is a follow-up visit at Week 60, 8 weeks after the Week 52 visit (12 weeks after the last dose of mepolizumab).

Eligible participants may enter an expanded access program (EAP), where available, immediately after completion of the 52-week study period. Participants who withdraw from the study prematurely will not be considered for an EAP.

Number of Participants:

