4. STUDY DESIGN

4.1. Overall Design

This is a 52-week, open-label, single arm, multicentre study of mepolizumab SC in children and adolescent participants with HES receiving SoC therapy.

Participants will be aged 6 to 17 years at Screening (Visit 1) and are expected to remain in the study for 52 weeks. Approximately 15 participants who are on a stable dose of HES therapy for at least 4 weeks prior to Visit 2 will be enrolled. Participants will have a 2- to 4-week run-in period for training and compliance on the use of their eDiary to record daily assessments. Eligible participants will receive the first dose of mepolizumab at Visit 2.

All participants will need to attend a study-site visit at Screening (Visit 1), Baseline (Visit 2), Week 4 (Visit 3), Week 8 (Visit 4), Week 24 (Visit 8), and the Week 52 exit visit (Visit 15). The other visits may be performed remotely where applicable country and local regulations allow. Home healthcare services may also be utilised to support these activities where local regulations and infrastructure allow. The last dose of mepolizumab will be given at Week 48 and the final visit of the treatment period will be at Week 52. There is a follow-up visit 8 weeks after the Week 52 visit (12 weeks after the last dose of mepolizumab). Protocol-defined eligible participants may enter an EAP, where available, immediately after completion of the 52-week study period (Section 6.6). Participants who enter the EAP will not need a study follow-up visit.

All participants will be on active treatment with mepolizumab. Investigators may adjust HES therapy (SoC) as needed from Visit 3 (4 weeks after the first dose of mepolizumab). All participants will be managed during the study according to routine medical care (i.e., participants and/or caregiver will be instructed to contact their investigator for evaluation or seek emergency care as necessary if they or their child experience worsening of symptoms as per their usual practice).

The investigators will use the CCI [REDACTED] to assess for the presence of a HES flare.

An Independent Data Monitoring Committee (IDMC) will be utilised during the study.

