4.4. End of Study Definition

The total study treatment duration is 52 weeks.

The end of the study is defined as the date of the last visit of the last participant in the study. A participant is considered to have completed the study if he/she has completed the last visit at Week 52, regardless of whether mepolizumab treatment was received during the entire study period. For participants who do not enter the expanded access program (EAP), the end of the study (EOS) will be considered the follow-up visit (visit 16). For participants who enter the EAP before the follow-up visit has occurred, the end of study (EOS) will be considered Week 52 (visit 15).

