8.3. Adverse Events, Serious Adverse Events, and Other Safety Reporting

The definitions of AEs or SAEs can be found in Section 10.3.

The definitions of device-related safety events, (adverse device effects [ADEs] and serious adverse device effects [SADEs]), can be found in Section 10.6. Device deficiencies are covered in Section 10.6.3.

AEs will be reported by the participant (or, when appropriate, by a caregiver, surrogate, or the participant's legally authorised representative).

The investigator and any qualified designees are responsible for detecting, documenting, and reporting events that meet the definition of an AE or SAE and remain responsible for following up AEs that are serious, considered related to the study intervention or the study, or that caused the participant to discontinue the study intervention (see Section 7).

The method of recording, evaluating, and assessing causality of AEs and SAEs and the procedures for completing and transmitting SAE reports are provided in Section 10.3.

8.3.1. Time Period and Frequency for Collecting Adverse Events and Serious Adverse Event Information

All SAEs will be collected from the start of study intervention until the follow-up visit at the time points specified in the SoA (Section 1.3). However, any SAEs assessed as related to study participation (e.g., study intervention, protocol-mandated procedures, invasive tests, or change in existing therapy) or related to a GSK product will be recorded from the time a participant consents to participate in the study.

All AEs will be collected from the start of intervention until the follow-up visit at the time points specified in the SoA (Section 1.3).

Medical occurrences that begin before the start of study intervention but after obtaining informed consent will be recorded as Medical History/Current Medical Conditions not as AEs.

All SAEs will be recorded and reported to the sponsor or designee immediately and under no circumstance should this exceed 24 hours, as indicated in Appendix 3. The investigator will submit any updated SAE data to the sponsor within 24 hours of it being available.

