9.4.4. Safety Analysis

AEs will be coded using the MedDRA coding dictionary and summarised by preferred term. SAEs pre-treatment and AEs and SAEs on-treatment and post-treatment will be summarised separately. Separate summaries will be provided for all AEs, drug-related AEs, SAEs, events of special interest and for AEs leading to permanent discontinuation of mepolizumab treatment or withdrawal from the study.

Immunogenicity data, ECG, vital signs, and laboratory data will be summarised descriptively.

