4.7. Safety Analyses

The safety analyses will be based on the full analysis set, unless otherwise specified.

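### Post-treatment adverse-event percentages count expanded-access entrants as event-free, although those who completed dosing have almost no post-treatment observation

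*SAP*

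**What the plan says.** SAP 6.2.2.3 sorts adverse events into pre-, on- and post-treatment phases. The post-treatment rule is "AE onset date > Date of last dose of study treatment + 28 days", with no upper limit. Protocol 9.4.4 makes this a reported category: "SAEs pre-treatment and AEs and SAEs on-treatment and post-treatment will be summarised separately".

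The dates that matter are:

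- Last scheduled dose (Protocol 4.1): "The last dose of mepolizumab will be given at Week 48".
- Follow-up for those who attend it (Protocol 1.1): "There is a follow-up visit at Week 60, 8 weeks after the Week 52 visit (12 weeks after the last dose of mepolizumab".
- EAP entrants (Protocol 4.1): "Participants who enter the EAP will not need a study follow-up visit". For those who enter before that visit has taken place, Protocol 4.4 says "the end of study (EOS) will be considered Week 52 (visit 15".
- AE collection (Protocol 8.3.1): "All AEs will be collected from the start of intervention until the follow-up visit at the time points specified in the SoA".

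On the denominator, SAP 4.7 says "The safety analyses will be based on the full analysis set, unless otherwise specified". SAP 3 admits anyone with one dose to that set. SAP 4.7.2 summarises AEs for all participants and refers to the sponsor's data standards. Neither it nor 6.2.2.3 names another denominator, an at-risk subset or an exposure adjustment for the post-treatment phase.

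**The concern.** A percentage of participants with a post-treatment event is interpretable only if those in the denominator could have been seen to have one. Here the phase opens, for a child who takes every dose, at the point where the study closes for EAP entrants. These children add to the denominator and can hardly add to the numerator. The reported incidence then depends partly on how many families take up the EAP, which has nothing to do with safety after stopping mepolizumab, and the distortion is always towards understatement.

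The same table would also mix very different lengths of observation. Participants who stop treatment early and remain to Week 52 have been past the boundary for weeks or months, and Protocol 6.6 allows them to be considered for the EAP as well. Neither a single count nor a single percentage shows this.

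**Working it through.** **Inputs.** Last dose at Week 48 (Protocol 4.1). Phase boundary at last dose + 28 days (SAP 6.2.2.3). End of study at Week 52 for EAP entrants (Protocol 4.4). Follow-up about 12 weeks after the last dose, with ±7 days at the Week 48, Week 52 and follow-up visits (Protocol Table 1). N = 15 (SAP 5). The number entering the EAP, k, is not in the documents and is varied as an assumption.

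**The plan's own dates.** 48 + 12 = Week 60, and 60 − 52 = 8 weeks. Both agree with Protocol 1.1.

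**Boundary.** Counting days from the first dose, 48 × 7 + 28 = 364 = 52 × 7, which is Week 52.

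**Post-treatment observation by type of participant.**

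- Full-course EAP entrant: 364 − 364 = 0 days on schedule. At the extreme, with the Week 48 dose 7 days early (day 329, boundary day 357) and the Week 52 visit 7 days late (day 371), 371 − 357 = 14 days.
- Full-course non-entrant: 60 × 7 − 364 = 56 days on schedule. With the follow-up window, 84 − 7 − 28 = 49 to 84 + 7 − 28 = 63 days.
- Early discontinuer who stays to Week 52: (364 − (7w + 28))/7 weeks when the last dose is at Week w. This gives 48 weeks for w = 0, 24 weeks for w = 24 and 4 weeks for w = 44.

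**Dilution.** Suppose k of 15 are full-course entrants with no post-treatment time and the other 15 − k are observed. With x affected children, the table shows x/15, while the proportion among those observed is x/(15 − k). The ratio is (15 − k)/15. For x = 1:

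| k (assumed) | Observed | Shown | Among observed | Ratio |
|---|---|---|---|---|
| 0 | 15 | 6.7% | 6.7% | 1.00 |
| 3 | 12 | 6.7% | 8.3% | 0.80 |
| 5 | 10 | 6.7% | 10.0% | 0.67 |
| 8 | 7 | 6.7% | 14.3% | 0.47 |
| 10 | 5 | 6.7% | 20.0% | 0.33 |
| 12 | 3 | 6.7% | 33.3% | 0.20 |

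**Why a changed headcount is not enough.** Take k = 5, with the 10 others on the 8-week schedule: 10 × 8 = 80 participant-weeks. If each entrant's visits slip so that they have 1 day past the boundary, all 15 count as observed and one case is again 1/15 = 6.7%. Participant-time barely moves: 80 + 5 × 1/7 = 80.7 weeks. A rate per participant-week is therefore robust to window slippage, and a headcount is not.

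**The case against.** The strongest objection is that the denominator is inferred. SAP 4.7 sets a default, SAP 4.7.2 defers to sponsor standards that are not in the documents, and no text names the denominator of the post-treatment table. That is fair. But a default applies unless something displaces it, and nothing in the SAP does. If the sponsor's standards already use an at-risk denominator, one sentence would settle the matter. SAP 6.1.1 does report off-treatment subject-years, but SAP 6.2.2.1 and 6.2.2.2 end the off-treatment phase at the Week 52 visit or withdrawal, so time in Weeks 52 to 60 would not be shown there.

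It can also be said that the trial is small and single-arm with no hypothesis test, that the follow-up waiver is deliberate, and that a child who resumes mepolizumab has no full off-drug period to observe. All of this stands. It limits the importance of the point, but it does not make an unobserved child event-free.

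Four stronger readings are tempting, and the documents do not support them:

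- That AEs between Week 52 and a later first EAP dose fall in no phase. SAP 6.2.2.3 has no upper limit, so any that are recorded are post-treatment. What is undefined is how long they are collected. Protocol 1.1 and 4.1 describe EAP entry as immediate, so a long gap is not the planned course, although Protocol 6.6 requires only that the first EAP dose precede the follow-up visit.
- That no entrant has a post-treatment period. This is nominally true only of those who complete dosing; early discontinuers who enter can have many weeks.
- That most completers will enter. Protocol 6.6 offers entry to eligible participants where a program exists, and no uptake is stated.
- That the plan promises safety data at 12 weeks after the last dose for everyone. Protocol 6.8 gives that purpose only for participants who must attend the follow-up visit.

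**Conclusion.** The point holds for the separate post-treatment AE and SAE summaries. Followed as written, the plan places full-course EAP entrants, with about 0 and at most about 14 days of post-treatment observation, in the same denominator as non-entrants with about 8 weeks and early discontinuers with up to about 48. Percentages are understated by the factor (15 − k)/15, which is 0.67 at k = 5 and 0.33 at k = 10.

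This rests on three assumptions: that the full-analysis-set default governs this table, that the k entrants have no post-treatment time, and that all others are observed past the boundary. Since k is unknown before the study ends, only a range can be given, and at k = 0 the effect vanishes. On-treatment AE percentages, the main safety output, do not change. The correction is worth making because it is cheap and, with 15 participants, a few unobserved children change the percentage visibly.

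**What to change.** In SAP 4.7.2 and 6.2.2.3, base the post-treatment AE and SAE summaries on participants observed beyond last dose + 28 days. Show that number, the participant-weeks of post-treatment observation and an exposure-adjusted rate. The participant-time is the essential part, because follow-up is very unequal and a headcount alone would re-admit entrants with a few days of visit slippage.

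Reconcile Protocol 4.4, which ends the study at Week 52 for entrants, with 8.3.1, which collects AEs until a follow-up visit that entrants do not have. The end of AE observation used to compute participant-time would then be defined for them.

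The SAP change costs one denominator and a few added rows in one set of tables. Its downside is a smaller post-treatment denominator, so the percentages will be coarser. Rewording the protocol would go through the amendment approval described in Protocol 10.1.1, so that part is more than an editorial change.
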